9.2. Rules for permanently interrupting study treatment

If a subject is withdrawn from the study before the full course of the treatment is completed, the physician must make all necessary arrangements to ensure that the subject receives the appropriate treatment for the relevant medical condition (e.g. with drug/s currently recommended by the national policy).

9.3. Subject withdrawal from the study and subject replacement

Subjects withdrawn from the study will not be replaced.

10. Data Analysis and Statistical Methods

10.1. Sample size determination

Samples size calculation is based on the efficacy (definitive cure) at 6 months (D210) which is the primary endpoint and main assessment criterion of interest.

The initial sample size assumptions were based on an expected efficacy at the end of 6 months follow-up of 93% for the tested combination and 91% for the reference arm SSG-PM, a non-inferiority margin of 7%, and 1.25% alpha (one-sided adjusted for multiplicity), the sample size required to reach a power of at least 80% per comparison of interest (each investigational arm vs SSG-PM) was 173 patients per arm rounded to 175. With the provision for lost to follow-up (LTFU), the original sample size for each arm was 192 (total of 576 patients).

In this revised protocol, the analysis will remain as planned, but comparison will be performed only between one investigational arm (arm 1 MF/PM 14 days) and the standard of care SSG-PM. Because the number of comparisons is now limited to one, there is no multiplicity of testing issue and therefore, no need for adjustment of type

Confidential Page 53 of 68

one error if the change in the protocol is not linked to an interim analysis or a shift to an adaptive design such as "drop the looser". Reasons for stopping a dose regimen is not based on significant data but rather related to the paucity of patients fulfilling inclusion criteria. Moreover, the number of patients who reached the primary time point was around 10% of the planned sample size and considering the expected success rate (93%), the number of observed failures cannot be informative unless it would have been a major discrepancy with expectation. Even if collected data are considered informative, the use of O'Brien Fleming curve in the alpha spending function when 10% of the sample size was available indicates that the fraction of alpha spent at the potential interim analysis becomes quite negligible at the final analysis. Consequently, no adjustment of alpha was considered necessary in the current situation. Using same assumptions for efficacy and non-inferiority margin, a power of at least 80%, and considering an alpha of 0.025 (one-sided, no adjustment for multiplicity) the required sample size is 153 patients per arm. A 10% provision for potential LTFU to ensure a power of at least 80% brings the sample size to 170 patients per arm (1 and 3).

The total number of patients included in the trial will be approximately 420, taking into account the number of patients randomized to treatment arm 2 before discontinuation of this arm (approximately 80 patients).

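### The 153 per arm that section 10.1 calls required does not come from the calculation behind its own 173: the named test needs 143 (144 by exact power), a conservative discrepancy that is not explained

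*Combined protocol and SAP*

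**What the plan says.** Section 10.1 of the protocol contains two sample sizes. The original one rests on "an expected efficacy at the end of 6 months follow-up of 93% for the tested combination and 91% for the reference arm SSG-PM", with "a non-inferiority margin of 7%, and 1.25% alpha (one-sided adjusted for multiplicity") and at least 80% power for each comparison with SSG-PM. The size required "was 173 patients per arm rounded to 175", and with a provision for loss to follow-up "the original sample size for each arm was 192 (total of 576 patients").

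The revised size, for the single comparison of arm 1 with arm 3, is introduced with "Using same assumptions for efficacy and non-inferiority margin, a power of at least 80"%, "considering an alpha of 0.025 (one-sided, no adjustment for multiplicity"), and the result is that "the required sample size is 153 patients per arm". A 10% provision for loss then brings this to 170 per arm. The same section says that the analysis stays as planned.

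Section 10.6 names the Blackwelder test as the primary test of non-inferiority, and section 6 gives 1:1 allocation. No formula or software is named for either sample size. The 170 is also the target in the synopsis and section 4, and the point at which recruitment stops in section 6.

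**The concern.** By the text of 10.1, the rates, the margin and the power are unchanged and only alpha moves, from 0.0125 to 0.025. A reader should therefore get from the first figure to the second by changing one normal quantile. That step does not lead to 153.

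What is at stake is whether the size justification can be reproduced, and whether the plan says correctly what the chosen size delivers. This version of the protocol was written because recruitment was slow, so a figure presented as the requirement should be the requirement. Validity and type I error are not affected.

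**Working it through.** **Inputs.** Cure 93% (test) and 91% (reference), margin 7 points, power 80%, one-sided alpha 0.0125 and then 0.025, all from section 10.1. Allocation 1:1 from section 6. Blackwelder test from section 10.6.

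**Formula.** With unpooled variance,

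n per arm = (z_alpha + z_beta)² × [0.93 × 0.07 + 0.91 × 0.09] / (0.93 − 0.91 + 0.07)²

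The bracket is 0.0651 + 0.0819 = 0.1470, and the denominator is 0.09² = 0.0081.

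**Step 1: the plan's first figure.** At alpha 0.0125, (2.2414 + 0.8416)² = 9.505, and 9.505 × 0.1470 / 0.0081 = 172.5, so 173. This matches the protocol.

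**Step 2: the same calculation at alpha 0.025.** (1.9600 + 0.8416)² = 7.849, and 7.849 × 0.1470 / 0.0081 = 142.4, so 143. The protocol states 153. By this formula, 153 per arm gives exactly 80% power at a one-sided alpha of about 0.0196, a value that the protocol does not mention.

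**Step 3: exact power of the same test.** Summing the binomial probabilities for the unpooled test at 0.025 gives 79.97% at 143 and 81.5% at 144. Exact power moves in a sawtooth: it first touches 80% at 138 but stays at or above it only from 144. At 0.0125 it stays at or above 80% from 173. So the exact reading also supports 173, and its counterpart at 0.025 is 144.

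**Step 4: other methods.** Required n per arm for 80% power:

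| Method | alpha 0.0125 | alpha 0.025 |
|---|---|---|
| Protocol | 173 | 153 |
| Blackwelder, normal formula | 173 | 143 |
| Blackwelder, exact power | 173 | 144 |
| Agresti-Caffo, exact power | 176 | 147 |
| Newcombe, exact power | 184 | 150 |
| Farrington-Manning score, exact power | 185 | 151 |
| Miettinen-Nurminen, exact power | 186 | 152 |
| Farrington-Manning score, asymptotic formula | 192 | 158 |
| Arcsine | 230 | 190 |

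A continuity-corrected formula gives 194.1 and 163.9 before rounding. No method tried gives both 173 and 153.

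**Step 5: what the chosen sizes deliver.** Normal-formula power at 0.025 is the normal probability below 0.09 / √(0.1470/n) − 1.960.
- n = 153: 2.9036 − 1.9600 = 0.9436, power 82.7% (exact 82.6%).
- n = 170: 3.0606 − 1.9600 = 1.1006, power 86.4% (exact 86.4%).

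**Step 6: the loss provision.** 153/0.9 = 170 and 170 × 0.9 = 153, so this arithmetic is right.

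**The case against.** The strongest reply is that 10.1 holds the efficacy and margin assumptions constant but does not promise the same formula or software. If 153 came from a score-type test judged by exact power, it is defensible: Farrington-Manning reaches 80% at 151 and Miettinen-Nurminen at 152, and both have 80.3% at 153. That part stands, and it rules out saying that 153 cannot follow from the stated rates, margin and alpha. It does not close the point, because at 0.0125 those tests need 185 and 186 and have only 76.9% power at 173. On that reading the method changed between two figures that the text presents as differing in alpha alone.

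It could also be said that 173 belongs to a superseded design. But 143 follows from the current assumptions and the currently named test without any use of 173; the older figure only helps to identify the formula.

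Three stronger readings are tempting, and the documents do not support them.
- A reader might infer that the stated power is wrong. It is not: 10.1 claims at least 80%, and 153 and 170 analysed per arm both meet that.
- A reader might infer that the loss allowance is wrong, or that 10% is a limit on loss. The arithmetic is correct, and the text calls it a provision, not a maximum.
- A reader might infer that the trial could stop at 143/0.9 = 159 per arm, or that 170 keeps 80% power down to 143 evaluable, a loss of 27/170 = 15.9%. Both treat lost patients as leaving the denominator. Section 10.6 does not: in the primary mITT analysis, loss at D56 or before counts as failure, and an unconfirmed status at D210 is imputed. Loss therefore acts mainly on the cure rates, not on n, and these statements do not describe the planned analysis.

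**Conclusion.** The point holds in a narrow form. Under the named Blackwelder test, with 93% against 91%, a 7% margin, one-sided 0.025 and 1:1 allocation, the required size is 143 per arm by the formula that gives 173, or 144 by exact power. The stated 153 is 9 to 10 per arm higher, and 10.1 does not say why. Either the method was changed without saying so or 153 is an error; the documents do not allow a choice between the two.

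The discrepancy is conservative. The trial is not underpowered on its assumptions: power is about 83% with 153 and 86% with 170 per arm in the analysis. Those figures assume that 93% and 91% are the cure rates as the mITT analysis counts them. This is a correction to the justification, not a threat to the trial's conclusion.

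**What to change.** In section 10.1, do one of two things:
- replace 153 with the figure from the method that gave 173, naming it (143 by the unpooled Blackwelder formula, or 144 by exact power); or
- name the formula or software behind 153 and restate the 0.0125 figure by that same method.

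In either case keep 170 per arm, and state what it gives: about 86% power with 170 per arm in the mITT analysis at 93% against 91%, one-sided 0.025. If 153 is replaced, present 170 as the chosen size, since it no longer follows from the required figure and the 10% provision.

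Do not add statements such as 83% power with 10% loss, or 80% power down to 16% loss, because section 10.6 counts early losses as failures and imputes later ones.

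The cost is one or two sentences in 10.1. The enrolment target, the recruitment stop and the analysis do not change, and no further patients are needed.

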10.2. Definition of study populations included in the analysis

The following patient populations will be defined for analysis:

- Intention-To-Treat (ITT): all randomized patients in the arms to which they were randomly assigned regardless of their adherence with the inclusion-exclusion criteria, the treatment they received, and subsequent withdrawal from treatment or deviation from the protocol.
- Modified Intention-To-Treat (mITT) or Full Analysis Set (FAS): All randomized
 patients receiving at least one dose of treatment. In case of error of treatment
 allocation, the actual treatment received will be used in the analysis. Modified ITT
 set of patients will be used in the primary efficacy analysis and in safety analysis.
- Set of completers: subset of patients belonging to the FAS, who attend the 6-months follow-up visit. This set will be used in a sensitivity analysis of the primary efficacy analysis. This analysis will be based on the definitive cures.
- Per protocol (PP) set of patients: subset of patients belonging to the FAS and who
 are free from major protocol violations. Major protocol violations are any violation
 which might bias the result of the non-inferiority test. Major violations will be defined
 a priori in the statistical analysis plan. They will be identified and documented
 during the blind review of data. This set of patients will be used in the primary
 sensitivity analysis.

The primary population for efficacy analysis at D210 will be the modified intention to treat population (mITT or FAS). Furthermore, per-protocol set of patients and the set of completers sensitivity analyses will be performed.

All patients enrolled in the study and who have been administered the first dose of study medication will be included in the safety analysis.

Confidential Page 54 of 68

For the secondary endpoint on PK, all subjects exposed to at least one dose of the medication and who have a PK sample collected will be included in the analysis.

Patients' data randomized in arm 2 (PM 14 days/MF 28 days), which recruitment is now discontinued, will be summarized in a descriptive analysis, but not included in the comparative efficacy analysis.

10.3. Subject Disposition

The number of patients who were screened, failed screening, randomized, completed the treatment period, completed the follow-up, early terminations and reasons for early termination of study will be summarized by number of patients (*n*) and percentages (%).

10.4. Baseline

Routine baseline characteristics including age, sex, height, weight, BMI for age*, and symptoms (fever, weight loss, epistaxis, etc.) will be documented and summarised as appropriate according to data variable type (e.g. mean for normally distributed continuous data).

* Note: for Ethiopia, MUAC will be documented in addition to BMI for age

10.5. Treatment Compliance

All test drugs will be supervised on administration by study medical staff. The dose given will be recorded in the patient dispensing log and in the CRF. Full compliance will be considered if 90-110% of the prescribed dose is administered.

10.6. Efficacy Analysis

Primary endpoint:

- Definitive cure or treatment success:
- absence of signs and symptoms of VL at D210,
- o no rescue treatment at any time up to D210 (included).
 - Treatment failure:
- o Patient who requires rescue treatment due to any of the following:
 - Initial failure:
 - occurrence of adverse events that leads to treatment discontinuation
 - relapse at any time;
- o death during treatment period or death during follow-up period that is related to VL
- Lost to follow-up at D56 or before.
 - Unconfirmed status at D210:

Confidential Page 55 of 68

 Patient who did not fail at day 28 (initial cure) and at day 56 (probable cure), did not relapse before D210 (no rescue treatment, no signs and symptoms of VL before day 210) and did not attend day 210 visit.

Definitions:

Initial failure: patient who did not respond to the treatment and required rescue therapy within the 28 days treatment period; or patient who had a positive parasitology (by microscopy) at the D28 assessment.

Relapse: patient who had responded to treatment and had a negative parasitology at the D28 assessment, but who presents signs and/or symptoms of VL during follow-up, with VL confirmed by presence of parasites in a parasitological investigation.

Secondary efficacy endpoints:

Initial cure - cure at the end of treatment (Day 28), defined as recovery of clinical signs and symptoms; absence of parasites (microscopy) and no rescue treatment administered at Day 28 or before.

Probable cure - absence of clinical signs and symptoms of VL at D56 and no prior requirement for rescue treatment.

Primary Efficacy Analysis

The primary efficacy analysis will be based on

- the modified intention to treat population (mITT or FAS);
- the primary endpoint (cure at D210);
- the primary imputation approach (see below) and the primary test of non-inferiority, which is the Blackwelder test.
- primary comparison: MF-PM 14 days vs SSG-PM.

The significance limit will be 0.025 (one-sided). If the non-inferiority test is significant the test of superiority will be performed.

Handling of unconfirmed status

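### The primary test is named only as the Blackwelder test; without a continuity correction its exact type I error at the design rates is about 2.75%, not 2.5%, and a score test would bring it close to the stated level at little cost

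*Combined protocol and SAP*

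**What the plan says.** Section 10.6 (Primary Efficacy Analysis) lists among the elements of the primary analysis the main non-inferiority test, "which is the Blackwelder test". The level is given in the same section: "The significance limit will be 0.025 (one-sided"). The variance estimate (pooled, unpooled or restricted to the null) is not stated, nor is a continuity correction. The five sensitivity analyses in section 10.6 change the imputation rule or the analysis set; none changes the test. The 95% confidence interval mentioned under the shift to superiority has no named method.

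Section 10.1 assumes cure rates of "93% for the tested combination and 91% for the reference arm SSG-PM, a non-inferiority margin of 7" per cent. For the revised two-arm comparison it states: "considering an alpha of 0.025 (one-sided, no adjustment for multiplicity) the required sample size is 153 patients per arm", for at least 80% power, and 170 per arm after a 10% provision for loss to follow-up. The formula is not named.

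**The concern.** The uncorrected Blackwelder statistic divides the observed difference plus the margin by a standard error computed from the observed proportions. When cure rates are high, that standard error tends to be too small in the samples that lead to rejection, so the test can reject more often than its nominal level.

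The error would go one way, towards declaring non-inferiority when MF/PM is truly 7 points worse. Section 10.1 argues at length for using the full one-sided 0.025 without adjustment, and section 1 says the result will support policy change in national control programmes. The sole primary test should therefore deliver roughly the level claimed, and no planned sensitivity analysis would show whether the choice of test matters.

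**Working it through.** **Inputs.** Expected cure 93% (MF/PM) and 91% (SSG-PM), margin 7 points, one-sided alpha 0.025, 153 and 170 per arm (section 10.1); 1:1 allocation (section 6). The null boundary at the design rate is 91% − 7% = 84% for MF/PM.

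**The plan's sample size.** The uncorrected normal formula is

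n = (z₁₋α + z₁₋β)² × [p_T(1−p_T) + p_C(1−p_C)] / (p_T − p_C + 0.07)².

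The variance sum is 0.0651 + 0.0819 = 0.1470 and the squared distance is 0.09² = 0.0081.
- Alpha 0.0125: (2.241 + 0.842)² × 0.1470/0.0081 = 172.5, so 173. This is the original figure exactly ("each investigational arm vs SSG-PM) was 173 patients per arm rounded to 175").
- Alpha 0.025: (1.960 + 0.842)² × 0.1470/0.0081 = 142.4, so 143, not 153.
- Other routes at alpha 0.025: pooled variance 143; continuity correction 164; asymptotic score formula 158. The smallest n with exact power of at least 80% is 151 (Farrington-Manning) or 152 (Miettinen-Nurminen).
- Dropout: 153/0.90 = 170, as stated.

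The stated 153 is therefore within two patients of an exact score calculation. That match came from trying several variants, so it does not show which method was used.

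**Exact size and power.** For each test, the binomial probabilities of all pairs (x_T, x_C) with Z ≥ 1.96 were summed:

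size = Σ Σ b(x_T; n, p_C − 0.07) · b(x_C; n, p_C) · 1{Z ≥ 1.96}.

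Power uses p_T = 0.93 and p_C = 0.91. The numerator of Z is p̂_T − p̂_C + 0.07. The uncorrected test uses the variance of the observed proportions, the corrected test subtracts 1/n from the numerator, and the score test uses the variance at the maximum-likelihood rates constrained to differ by 7 points.

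| Test | n per arm | Size at 91/84 | Size at 95/88 | Size at 97/90 | Power at 91/93 |
|---|---|---|---|---|---|
| Uncorrected | 153 | 2.73% | 2.97% | 3.52% | 82.6% |
| Uncorrected | 170 | 2.76% | 2.95% | 3.31% | 86.4% |
| Continuity-corrected | 153 | 1.85% | | | 77.9% |
| Continuity-corrected | 170 | 1.88% | | | 82.5% |
| Score (Farrington-Manning) | 153 | 2.48% | 2.30% | 2.13% | 80.3% |
| Score (Farrington-Manning) | 170 | 2.42% | 2.40% | 2.26% | 84.7% |

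Pooled and unpooled variances give the same uncorrected results. The excess at the design rate is 2.73 − 2.50 = 0.23 points at 153 and 2.76 − 2.50 = 0.26 points at 170, or 9 to 10% in relative terms. Over all n from 150 to 175 per arm, the uncorrected size at 91/84 lies between 2.66% and 2.87%.

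**With the planned imputation.** The 1 − 2P_R rule was simulated at 170 per arm, assuming 0 to 5% unconfirmed status and 30 to 60% of failures after D56 (neither figure is in the protocol). Size was 2.6 to 2.8% uncorrected and 2.3 to 2.4% for the score test, so the imputation penalty does not remove the excess.

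**A result where the choice decides.** Take 162/170 cures on SSG-PM and 159/170 on MF/PM. The numerator is −3/170 + 0.07 = 0.0524. The uncorrected standard error is √[(0.9353×0.0647 + 0.9529×0.0471)/170] = 0.0249, so Z = 2.10 and non-inferiority is declared. The constrained rates are 0.8965 and 0.9665, the score standard error is 0.0271, and Z = 1.93, so it is not declared; the score test needs 160 cures. The control rate in this example, 95.3%, is above the plan's 91%.

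**The case against.** The strongest reply is that the protocol does not say which form it means, so calling the test wrong as written goes too far. That stands. With a continuity correction the level is held, and section 10.2 refers to a statistical analysis plan that may fix the form. The original 173 agrees with the uncorrected formula, which is indirect support for that reading but not proof.

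A reader might also infer that the true error rate is 3.3 to 3.5%. The documents do not support this. Those figures need a 97% cure rate on SSG-PM, whereas sections 3.3 and 10.1 assume 91%. Counting losses by D56 as failures and imputing with a penalty push the analysed rates lower, not higher. With 86% control cure the uncorrected size is only 2.69% (153 per arm) or 2.58% (170).

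The score test does not guarantee the level either. It reaches 2.52% at 153 per arm for control rates of 88 to 89%, and 2.55% in a wider scan (150 to 175 per arm, control rates 85 to 97%). It is closer to nominal, not exact.

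Finally, the Blackwelder test is a named, prespecified method, and an excess of 0.25 points is ordinary error for a large-sample test. At the design rates with 170 per arm the two tests disagree in only 86.4 − 84.7 = 1.7% of trials. This limits the weight of the point. It does not remove it, because the alternative costs little.

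**Conclusion.** The point holds as a cheap improvement to the primary test and as a request to specify it fully. If the Blackwelder test is used without a continuity correction, its exact type I error at the plan's own boundary is 2.73% (153 per arm) to 2.76% (170 per arm), against a stated 2.5%, in the direction of a false non-inferiority claim. It would be larger only if SSG-PM cured clearly more than the assumed 91%: about 3.0% at 95%, and 3.3 to 3.5% at 97%.

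This rests on binomial outcomes, equal arms, the 7-point margin and a critical value of 1.96. It does not show that the plan is invalid, or that the sponsor has chosen the uncorrected form. The power figures take the 93% and 91% cure rates as the analysed rates. Counting patients lost by D56 as failures would lower power for either test: to about 76% (uncorrected) and 74% (score) at 170 per arm if 3% were lost in both arms, an assumed rate. That loss comes from the endpoint rule and is separate from this point.

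**What to change.** In section 10.6, or in the statistical analysis plan, name the Farrington-Manning score test at one-sided 0.025 as the primary non-inferiority test, reported with the Miettinen-Nurminen 95% interval for the difference in cure rates. The two differ by a small variance factor and can part at the boundary (size at 170 per arm 2.42% and 2.39%), so state which one governs the decision. Keep the Blackwelder test as a sensitivity analysis, with its variance form and any continuity correction written out. State in section 10.1 which method gave 153.

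The cost is wording and some power: 82.6% to 80.3% at 153 per arm, and 86.4% to 84.7% at 170. Both stay at or above the stated 80%. The margin at 153 is thin, since the normal approximation for the score test gives 78.8% there; at 170 it gives 83.0%. If the sponsor keeps the Blackwelder test as primary with a continuity correction, the level is held, but exact power at 153 per arm is 77.9% (82.5% at 170).
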